4.0 Study Schedules

4.1 Test schedule

Tests and Procedures	Screening prior to registration	Active Treatment			End of Treatment	
		D1 of each cycle	D8 of Cycle 1 only	Every 2 cycles	End of Treatment	Safety follow up: 30 days post treatment
window		±7 days	±3 days	±7 days	±7 days	±7 days
History and exam, Wt, PS	X	X	X		X	X
Height	X					
Adverse event assessment	X	X	X		X	X
Pregnancy test ¹	X					
Hematology: CBC with differential	X	X	X		X	X
Chemistry ²	X	X	X		X	X
CA19-9 ³		X		X ⁴	X	
Tumor imaging - CT (chest, abdomen, pelvis) or CT (chest) and MRI (abdomen, pelvis)	X ⁵			X ⁶	X	
Research blood specimens ^{7,R}		X			X	
Patient Medication Diary (Appendix II) ⁸		X				

Cycle = 28 days; R=Research funded

¹ For persons of childbearing potential only. Must be done ≤7 days prior to registration.

² Chemistry: Na, K, albumin, AST, ALT, alkaline phosphatase, total and direct bilirubin, creatinine

³ Baseline prior to Cycle 1, Day 1, then every two cycles or as clinically indicated

⁴ To be performed ≤7 days prior to planned Day 1 of odd numbered cycles (Cycle 3, 5, 7 etc) or as clinically indicated

⁵ Can be performed ≤28 days prior registration

⁶ To be performed ≤7 days prior to planned Day 1 of odd numbered cycles (Cycle 3, 5, 7 etc) or as clinically indicated

⁷ Research blood specimens to be collected on Cycle 1 Day 1 (or any time between registration and Cycle 1 Day 1), Cycle 3 Day 1 and end of treatment (see [Section 14.0](#))

⁸ The diary must begin the day the patient starts taking the medication and must be completed per protocol and returned to the treating institution

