3.0 Patient Eligibility

3.1 Registration – Inclusion Criteria

3.11 Age \geq 18 years.

3.12 Histological confirmation of advanced biliary tract cancers including cancers originating in gallbladder who have received at least one line of systemic anticancer therapy.
Note: Patients who have either progressed or are intolerant to the prior therapy can be included in this study.

3.13 Measurable disease as defined in [Section 11.0](#).

3.14 ECOG Performance Status (PS) 0 or 1 ([Appendix I](#)).

3.15 The following laboratory values obtained \leq 21 days prior to registration.

- Absolute neutrophil count (ANC) \geq 1500/mm³
- Platelet count \geq 100,000/mm³
- Total bilirubin \leq 1.5 \times upper limit of normal (ULN)
- Aspartate transaminase (AST) or Alanine transaminase (ALT) \leq 3 \times ULN
- Creatinine \leq 1.5 \times ULN

3.16 Negative pregnancy test done \leq 7 days prior to registration, for persons of childbearing potential only.

3.17a Provide written informed consent.

3.17b Willing to return to enrolling institution for follow-up (during the Active Monitoring Phase of the study).

3.17c Willing to provide blood samples for correlative research purposes.

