3.2 Registration – Exclusion Criteria

3.21 Any of the following because this study involves an agent that has potential genotoxic, mutagenic and teratogenic effects:

- Pregnant persons
- Nursing persons
- Persons of childbearing potential who are unwilling to employ adequate contraception for at least 3 months after the last dose of the study drug

3.22 Co-morbid systemic illnesses or other severe concurrent disease which, in the judgment of the investigator, would make the patient inappropriate for entry into this study or interfere significantly with the proper assessment of safety and toxicity of the prescribed regimens.

3.23 Immunocompromised patients and patients known to be HIV positive and currently receiving antiretroviral therapy. NOTE: Patients known to be HIV positive, but without clinical evidence of an immunocompromised state, are eligible for this trial.

3.24 Uncontrolled intercurrent illness including, but not limited to, ongoing or active infection, symptomatic congestive heart failure, unstable angina pectoris, cardiac arrhythmia, or psychiatric illness/social situations that would limit compliance with study requirements.

3.25 Receiving any other investigational agent which would be considered as a treatment for the primary neoplasm \leq 21 days prior to registration..

- 3.26 Receiving any anticancer therapy for biliary tract cancer \leq 21 days prior to registration.
- 3.27 Other active malignancy requiring treatment in \leq 6 months prior to registration.
EXCEPTIONS: Non-melanotic skin cancer or carcinoma-in-situ of the cervix.
NOTE: If there is a history of prior malignancy, they must not be receiving other specific treatment for their cancer.
- 3.28 History of myocardial infarction \leq 6 months prior to registration, or congestive heart failure requiring use of ongoing maintenance therapy for life-threatening ventricular arrhythmias.

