6.6 Treatment start

Treatment cannot begin prior to registration and must begin ≤ 28 days after registration.

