6.7 Pretreatment

Pretreatment tests/procedures (see [Section 4.0](#)) must be completed within the guidelines specified on the test schedule.

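### The 7-day pregnancy-test limit runs to registration rather than first dose, so a potentially teratogenic drug may be started on a test up to 35 days old with no repeat scheduled

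*Combined protocol and SAP*

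**What the plan says.** Inclusion criterion 3.16 requires a negative pregnancy test no more than 7 "days prior to registration, for persons of childbearing potential only". Footnote 1 to the test schedule in 4.1 repeats the limit: "Must be done ≤7 days prior to registration". The row for this test has one mark, in the screening column that precedes registration. There is none on Day 1 of any cycle, at end of treatment or at safety follow-up.

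The interval from registration to dosing is governed by 6.6: "Treatment cannot begin prior to registration and must begin ≤ 28 days after registration". Section 6.7 adds no test of its own. It says only that pretreatment procedures "must be completed within the guidelines specified on the test schedule".

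The reason for excluding pregnant persons is given in 3.21: "this study involves an agent that has potential genotoxic, mutagenic and teratogenic effects".

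**The concern.** A 7-day limit on a pregnancy test makes sense if its aim is a recent negative result when the fetus could first be exposed. Exposure starts with the first dose, whereas this limit is measured to registration, which can be four weeks earlier. A pregnancy that becomes detectable between the screening test and Cycle 1 Day 1 need not be looked for before the drug is given, and the site would have followed the protocol in full. What is at stake is avoidable fetal exposure to a drug that the protocol itself treats as potentially teratogenic. The efficacy result is not at stake.

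**Working it through.** The documents state no figure for the interval from test to dose, so there is none to reproduce. It follows from two limits.

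**Inputs**
- a = days from pregnancy test to registration: 0 to 7 (3.16; 4.1 footnote 1).
- b = days from registration to first dose: 0 to 28 (6.6).
- Pregnancy tests scheduled between registration and first dose: none (4.1 table; 6.7 adds nothing).

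**Formula.** Age of the test at first dose = a + b.

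**Maximum.** 7 + 28 = 35 days. The ±7-day visit window on Day 1 does not lengthen this, because 6.6 is a firm limit.

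**By start day**

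| First dose, days after registration (b) | Test age at first dose (b to b + 7) | More than 7 days old? |
|---|---|---|
| 0 | 0–7 | Never |
| 7 | 7–14 | Unless tested on the day of registration |
| 8 | 8–15 | Always |
| 14 | 14–21 | Always |
| 28 | 28–35 | Always |

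For b = 1 to 7 the age exceeds 7 days only if a > 7 − b. For b ≥ 8 it exceeds 7 days for every a, including a = 0. Those values, 8 to 28, are 21 of the 29 permitted values of b (0 to 28). This counts what the rule permits. It does not estimate the share of patients affected.

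**Could another provision supply the missing test?**
- Day 1 chemistry does not. Footnote 2 lists the panel in full, "Chemistry: Na, K, albumin, AST, ALT, alkaline phosphatase, total and direct bilirubin, creatinine", and it contains no pregnancy test.
- The eligibility rule does not. Section 13.5 judges eligibility as of registration, so a pregnancy arising later does not make the patient ineligible.
- The pregnancy provisions in 10.51, 10.55 and 10.83 do not. They cover reporting, and stopping treatment once a pregnancy is known, and they schedule no test.

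**With the limit also tied to first dose.** Either a + b ≤ 7 already, or a repeat test brings the age to 7 days or less. The maximum falls from 35 to 7 days.

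**The case against.** The arithmetic and the absence of a later test are not in dispute. The case on the other side concerns how much this matters.

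- **It is a consistent convention.** Screening windows generally run to registration: laboratory values 21 days, imaging 28 days, and prior therapy 21 days. The pregnancy test follows suit, with a tighter limit than any of these. This shows that the wording is a choice and not a slip. It does not make registration the right reference point for fetal exposure. That the limit is meant to give a recent result at exposure is an inference from 3.21; the protocol does not say so.
- **Repeating hematology and chemistry on Day 1 proves little.** Day 1 counts are needed for the dosing rules in 8.3, so their repetition does not show that screening tests in general were meant to be redone. That is right, and the point does not rest on this comparison. The Day 1 blood work matters only because it makes a repeat test easy to add.
- **Few patients are exposed to the gap.** Section 16.73 projects 14 women among 28 patients. Those affected are the subset who are of childbearing potential, start late enough, and become detectably pregnant in between. The primary endpoint is counted from registration (16.21), which also gives some reason to start promptly. This stands and limits the size of the concern.
- **Other safeguards exist.** The contraception bullet in 3.21 states no start point and can be read as covering treatment. A history and examination are scheduled on Day 1, and a known pregnancy stops treatment. These lower the risk, but none confirms pregnancy status before dosing, and the protocol evidently did not regard contraception alone as enough, since it asks for a test as well.
- **The fix covers only the first dose.** With no later testing, a patient tested within 7 days before Cycle 1 would reach an undelayed Cycle 2 Day 1 on a test 28 to 35 days old (28 + 0 to 28 + 7). This is true, and testing during treatment is a separate question. It is no reason to leave the first exposure uncovered when the protocol already sets a 7-day limit.

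**Conclusion.** The concern holds. The protocol permits a first dose on a pregnancy test up to 35 days old, without a deviation and without a scheduled repeat. For any start from day 8 to day 28 after registration, the result is always more than 7 days old.

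The conclusion rests on 3.16, footnote 1 and 6.6 as written, and on no other section requiring a test before dosing. It does not depend on how the contraception bullet is read. The 35 days is the permitted maximum and not the expected interval. The documents give neither the usual time from registration to dosing nor the number of persons of childbearing potential, so the number affected is unknown and may be small.

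This is a patient-safety gap in scheduling, with no bearing on power, significance level or interpretation. The potential harm is serious and the remedy is cheap, so the change should be made.

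**What to change.** Reword 3.16 and footnote 1 of 4.1 along these lines: *A negative pregnancy test is required within 7 days before registration and within 7 days before the first dose. One test may serve both purposes; otherwise repeat it on or before Cycle 1 Day 1, with the result known before the first dose is taken.* Add a matching conditional mark at Cycle 1 Day 1 in the 4.1 table. As a secondary clarification, state in 3.21 when contraception must begin.

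The cost is protocol wording plus one routine test, needed only for persons of childbearing potential who start more than 7 days after the screening test. Cycle 1 Day 1 already includes a visit with hematology and chemistry, and footnote 7 already places a research blood draw on that day or between registration and it. Endpoint, sample size and analysis do not change. The change limits the age of the test at first dose; it will not detect very early conceptions or pregnancies that begin during treatment.

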4.2 Event Monitoring/Survival Follow-up

	Event Monitoring Phase ¹				
	q. 3 months until PD	At PD	After PD q. 3 months	Death	New Primary
Event Monitoring	X	X	X	X	At each occurrence

1. If a patient is still alive 2 years after registration, no further follow-up is required.

5.0 Stratification Factors OR Grouping Factor:

None

6.0 Registration Procedures

6.1 To register a patient

To register a patient, access the Mayo Clinic Cancer Center (MCCC) web page and enter the remote registration/randomization application. The registration/randomization application is available 24 hours a day, 7 days a week. Back up and/or system support contact information is available on the Web site. If unable to access the Web site, call the MCCC Registration Office at [REDACTED] between the hours of 8 a.m. and 5:00 p.m. Central Time (Monday through Friday).

The instructions for the registration/randomization application are available on the MCCC web page [REDACTED] and detail the process for completing and confirming patient registration. Prior to initiation of protocol treatment, this process must be completed in its entirety and a MCCC subject ID number must be available as noted in the instructions. It is the responsibility of the individual and institution registering the patient to confirm the process has been successfully completed prior to release of the study agent. Patient registration via the registration/randomization application can be confirmed in any of the following ways:

- Contact the MCCC Registration Office [REDACTED] If the patient was fully registered, the MCCC Registration Office staff can access the information from the centralized database and confirm the registration.
- Refer to “Instructions for Remote Registration” in section “Finding/Displaying Information about A Registered Subject.”

6.2 Verification

Prior to accepting the registration, registration/randomization application will verify the following:

- IRB approval at the registering institution
- Patient eligibility
- Existence of a signed consent form
- Existence of a signed authorization for use and disclosure of protected health information

6.3 Documentation of IRB approval

Documentation of IRB approval must be on file in the Registration Office before an investigator may register any patients.

In addition to submitting initial IRB approval documents, ongoing IRB approval documentation must be on file (no less than annually) at the Registration Office ([contact]). If the necessary documentation is not submitted in advance of attempting patient registration, the registration will not be accepted and the patient may not be enrolled in the protocol until the situation is resolved.

When the study has been permanently closed to patient enrollment, submission of annual IRB approvals to the Registration Office is no longer necessary.

6.4 Correlative studies

A mandatory translational research component is part of this study; the patient will be automatically registered onto this component ([Sections 3.17c, 14.0](#)).

6.5 Treatment on protocol

Treatment on this protocol must commence at Mayo Clinic under the supervision of a medical oncologist.

6.6 Treatment start

Treatment cannot begin prior to registration and must begin ≤ 28 days after registration.

6.7 Pretreatment

Pretreatment tests/procedures (see [Section 4.0](#)) must be completed within the guidelines specified on the test schedule.

6.8 Baseline symptoms

All required baseline symptoms (see [Section 10.6](#)) must be documented and graded.

6.9 Study Conduct

The clinical trial will be conducted in compliance with regulations (21 CFR 312, 50, and 56), guidelines for Good Clinical Practice (ICH Guidance E6), and in accordance with general ethical principles outlined in the Declaration of Helsinki; informed consent will be obtained from all participating patients; the protocol and any amendments will be subject to approval by the designated IRB prior to implementation, in accordance with 21 CFR 56.103(a); and subject records will be stored in a secure location and subject confidentiality will be maintained. The investigator will be thoroughly familiar with the appropriate use of the study drug as described in the protocol and Investigator's Brochure. Essential clinical documents will be maintained to demonstrate the validity of the study and the integrity of the data collected. Master files should be established at the beginning of the study, maintained for the duration of the study and retained according to the appropriate regulations.

7.0 Protocol Treatment

All patients will receive study medication FTD/TPI (TAS-102) in a 28-day treatment cycle. FTD/TPI (TAS-102) is available in 15 and 20 mg tablets. Study medication should be administered as outlined in the protocol.

7.1 Treatment Schedule

Use actual weight or estimated dry weight if fluid retention. BSA needs to be rounded to 2 decimal places. The study medication needs to be stored at the room temperature.

FTD/TPI (TAS-102) is administered in 28-day cycle. The starting dose of FTD/TPI (TAS-102) is 35 mg/m². The study drug will be administered on Days 1-5 and 8-12 of 28-day cycle. The treatment regimen consists of following:

Agent	Route	Day	Starting Dose
FTD/TPI (TAS-102)	PO	1-5	35 mg/m ² /dose twice daily
None		6-7	No treatment
FTD/TPI (TAS-102)	PO	8-12	35 mg/m ² /dose twice daily
None		13-28	No treatment

The study drug dose calculation based on BSA is as follows:

FTD/TPI (TAS-102) dose (twice daily)	BSA (m ²)	Dosage in mg (twice daily)	Tablets per dose	
			15 mg	20 mg
35 mg/m ²	<1.07	35	1	1
35 mg/m ²	1.07-1.22	40	0	2
35 mg/m ²	1.23-1.37	45	3	0
35 mg/m ²	1.38-1.52	50	2	1
35 mg/m ²	1.53-1.68	55	1	2
35 mg/m ²	1.69-1.83	60	0	3
35 mg/m ²	1.84-1.98	65	3	1
35 mg/m ²	1.99-2.14	70	2	2
35 mg/m ²	2.15-2.29	75	1	3
35 mg/m ²	≥2.30	80	0	4

7.2 Self-administration statement

Patients can be instructed in administration techniques and granted treatment independence. Any missed doses will be recorded. Patients will be instructed to:

- Store the study medication at room temperature
- Take the study medication on schedule
- Report any missed doses
- Take study medication within 1 hour after completing morning or evening meals with a glass of water
- If the patient vomits after taking the study medication, the dose should not be replaced.
- Return the unused medication at end of every cycle.
- If a patient forgets to take a dose (morning or evening), the missed dose should not be made up

7.3 Treatment by local medical doctor

Treatment by a local medical doctor (LMD) is not allowed on this study.

8.0 Dosage Modification Based on Adverse Events

For the first two cycles, strictly follow the modifications in this table. Thereafter, these modifications should be regarded as guidelines to produce mild-to-moderate, but not debilitating, side effects. Under exceptional circumstances, at the investigator discretion (in consultation with principal investigator) dose modifications or treatment interruption or continuation can be considered if it's considered to be in the best interest of a patient. If multiple adverse events are seen, administer dose based on greatest reduction required for any single adverse event observed. Reductions apply to treatment given in the preceding cycle and are based on adverse events observed since the prior dose. The criteria for dose modifications of FTD/TPI (TAS-102) for toxicities will be considered if an adverse event is at least possibly related to FTD/TPI (TAS-102).

NCI Common Terminology Criteria for Adverse Events (CTCAE) current version 4.0* will be utilized for dose modification unless otherwise specified. Up to three dose level reductions are allowed. Once reduced for an adverse event, no increase in dose of TAS-102 will be allowed.

* Located at http://ctep.cancer.gov/protocolDevelopment/electronic_applications.ctc.htm

8.1 Dose Levels (Based on Adverse Events in Section 8.2 and 8.3)

8.11 FTD/TPI (TAS-102) dose levels

Dose Level	FTD/TPI (TAS-102)
0*	35 mg/m ² /dose
-1	30 mg/m ² /dose
-2	25 mg/m ² /dose
-3	20 mg/m ² /dose

*Dose level 0 refers to the starting dose.

NOTE: Adverse events requiring a dose-reduction step for any or all drugs beyond the three dose-reduction steps (levels -1, -2 and -3) will be at the discretion of the treating physician, if the decision is made for the patient to be kept on study. These dose reductions must be clearly recorded in reported clinical data.

8.12 The study drug dose calculation after dose modifications based on BSA is as follows:

FTD/TPI (TAS-102) dose (twice daily)	BSA (m ²)	Dosage in mg (twice daily)	Tablets per dose	
			15 mg	20 mg
Dose Level -1 (30 mg/m ²)	<1.09	30	2	0
	1.09-1.24	35	1	1
	1.25-1.39	40	0	2
	1.40-1.54	45	3	0
	1.55-1.69	50	2	1
	1.70-1.94	55	1	2

FTD/TPI (TAS-102) dose (twice daily)	BSA (m ²)	Dosage in mg (twice daily)	Tablets per dose	
			15 mg	20 mg
Dose Level -2 (25 mg/m ²)	1.95-2.09	60	0	3
	2.10-2.28	65	3	1
	≥2.29	70	2	2
Dose Level -3 (20 mg/m ²)	<1.10	25 ¹	2 (PM) ¹	1 (AM) ¹
	1.10-1.29	30	2	0
	1.30-1.49	35	1	1
	1.50-1.69	40	0	2
	1.70-1.89	45	3	0
	1.90-2.09	50	2	1
	2.10-2.29	55	1	2
	≥2.30	60	0	3
	<1.14	20	0	1
	1.14-1.34	25 ¹	2 (PM) ¹	1 (AM) ¹
	1.35-1.59	30	2	0
	1.60-1.94	35	1	1
	1.95-2.09	40	0	2
	2.10-2.29	45	3	0
	≥2.30	50	2	1

¹For the total daily dose of 50 mg, patients should take 1 × 20-mg tablet in the morning and 2 × 15-mg tablets in the evening.

8.2 Dose Modifications Based on Interval Adverse Events during the cycle

8.21 For non-specified adverse events the following criteria for dose modification will be used for adverse events occurring during the cycle:

CTCAE Adverse Events ¹	Action for FTD/TPI (TAS-102)
Grade 1 or 2	Treat as scheduled
Grade 3 or 4	Hold treatment until resolved to ≤Grade 2 Reduce the dose by one dose level

¹ Except for alopecia, clinically insignificant laboratory abnormalities, and inadequately treated nausea, vomiting and diarrhea.

8.22 For specified adverse events following criteria for dose modification will be used for adverse events occurring during the cycle:

CTCAE Adverse Events	Action for FTD/TPI (TAS-102)
Neutrophil count decreased $<500/\text{mm}^3$	Hold treatment for the duration of the cycle
Platelet count decreased $<50,000/\text{mm}^3$	Hold treatment for the duration of the cycle

G-CSF can be used in this trial at the discretion of treating physician (see [Section 9.2](#))

8.3 Dose Modifications at the Time of Retreatment (Beginning of new cycle)

8.31 The dose modification guidelines for FTD/TPI (TAS-102) for non-specified adverse events on **Day 1** of each cycle of the treatment is mentioned below:

CTCAE Adverse Events ¹	Action for FTD/TPI (TAS-102)
Grade 1 or 2	Treat as scheduled
Grade 3 or 4	Delay Treatment until resolve to \leq Grade 2. Reduce the dose by one dose level.

¹ Except for alopecia, clinically insignificant laboratory abnormalities, and inadequately treated nausea, vomiting and diarrhea.

8.32 The dose modification guidelines for FTD/TPI (TAS-102) for specified adverse events on **Day 1** of each cycle of the treatment is mentioned below:

CTCAE { Adverse Events	Action for FTD/TPI (TAS-102)
Neutrophil count decreased $<1,500/\text{mm}^3$	Delay treatment by 1 week Reduce dose by one dose level for next treatment only if febrile neutropenia or uncomplicated Grade 4 neutropenia occurs that requires more than one week delay in start of next cycle
Platelet count decreased $<75,000/\text{mm}^3$	Delay treatment by 1 week Reduce dose by one dose level for next treatment only if Grade 4 thrombocytopenia occurs that requires more than one week delay in start of next cycle

